## 6.0 STATISTICAL CONSIDERATIONS

**Power for primary outcome.** Our primary outcome that we are using to power the study is reduction in pain interference. Based on PROMIS validation studies with chronic pain samples, a difference of 3 points or more between study arms was considered to indicate a clinically meaningful difference. The PROMIS website also gives the mean and standard deviation of the T-score metric ( $M = 50$ ,  $SD = 10$ ). We powered the analysis to be able to detect a 3-point difference (an effect size of  $d = .30$ ) between control and ET-LT, and then the same magnitude of effect between ET-LT and ET-SS (an effect size of  $d = .60$  for control versus ET-SS). Across 10,000 LMEM simulations, a post-attrition- $N = 255$ , we would have power  $>80\%$  to detect the study arm X time interaction.

**Missingness.** Data are likely to be missing not-at-random. This may lead to biased parameter estimates. Pattern-mixture modeling will test the sensitivity of our intervention analysis to missing data assumptions, by conducting sensitivity analyses after imputing missing data with a range of clinically plausible values using assumptions for missing data (e.g. best or worst case, with and without multiple imputation). With regard to survey data, in the previous ET trial, 353 of 390 participants (90.51%) completed the 6-month survey and 310 of 390 (79.49%) completed the 12-month survey. In completed surveys, data were missing on about 2% of core items. We expect similar rates in this study, that is, about 87% survey completion at 8 months. Thus, we increased the total sample size after attrition to 291 to increase the likelihood of detecting effects on the outcomes with 2 moderators: sex and number of chronic conditions.

**Quantitative analysis plan.** Intention-to-treat will be the data primary analyses.

**Assumptions and randomization effect.** We will report descriptive statistics for all demographic and clinical variables in both arms to ensure that randomization produced comparable groups; if not, variables with significant differences will be included as covariates in a sensitivity analysis. Sensitivity analyses (with and without covariate adjustment) will determine the robustness of covariate-related error control. All outcome variables will be examined using standard summary statistics, visualizations, and tests for normality and

homoscedasticity. Data will be transformed for continuous outcomes that do not meet the assumptions of a normally distributed outcome. We will test for a main effect of clinic site. If significant, we will add clinic site to our models to control for its variance.

*Effectiveness of control vs. ET-LT vs. ET-SS.* Linear mixed effects models (LMM)—which account for dependence among successive observations for the same participant and can address incomplete data—will be used to examine effects of study arm (ET-SS vs. ET-LT vs. control, a between-subjects factor) on our outcomes over time. We will conduct specific treatment X time contrasts both between, and within, groups to test time-based effects. For binary, count, and other non-normal data, generalized mixed effects models will be used.

*Mediation and moderation effects.* Structural equation modeling (SEM) will explore the effects of mediation on the relation between study arms and our two primary outcomes. We anticipate that the impact of study arm on pain interference and psychological QOL will be mediated by SDT (competence, relatedness, and motivation), exercise, and pain catastrophizing at 4 months. SEMs involving ET use will be run separately for just the ET-SS and ET-LT arms. 2) We anticipate that sex, number of chronic conditions, and barriers to technology will moderate the indirect paths of the mediation models (see Figure 1, logic diagram).

*Impact of interim analyses on Type 1 error for whole sample analysis.* Findings that are significant in the interim but not the final analyses will be treated as non-significant. The final analysis will examine all data over time. For analyses that address the same hypothesis a Holm-Bonferroni correction will be applied.

**Qualitative analyses.** For each data set, a coding scheme of key themes will be constructed, based on the research questions (perceived benefits, barriers to use) and examination of the data. Each scheme will be pilot tested, then 2 trained coders will code an overlapping subsample of 20% of content. Once reliability is established (minimum Krippendorff's alpha of .80 per category), the coders will work independently in NVivo.

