#### **Specific Aim 2: Conduct a randomized clinical trial to test the following hypotheses.**

Figure 1 describes the 3-arm RCT. Baseline covariates include race/ethnicity, education, baseline outcomes, life stresses, health service use, and technology use.

1. Primary outcomes: For those in ET-SS (vs. ET-LT vs. Control): pain interference will decrease and psychosocial quality of life will increase.

2. Secondary outcomes: ET-SS (vs. ET-LT vs. Control) will increase ET use at 8 months, increase physical quality of life, well-being, and communication with doctor. Pain intensity, 30-day hospital readmission rates, health distress, loneliness, and

[figure not shown]

Figure 1. Logic Diagram

irritability will decrease. We also plan to compare ET-LT to the UC control, given the unique focus of chronic pain in this study.

3. **Mediators:** Self-Determination Theory constructs of competence, social relatedness, and intrinsic motivation, together with exercise and pain catastrophizing, will mediate the effects of study arms on outcomes.

Additionally, use of ET at 4 months will mediate effects of study arms (ET-LT vs. ET-SS) on 8-month ET use.

4. **Moderators:** ET-SS (vs. ET-LT vs. Control) will show greater improvements for a) women (vs. men), b) patients with more (vs. fewer) chronic conditions, and c) patients with fewer barriers to using technology for the primary and secondary outcomes.

5. **Exploratory analyses:** We will measure level of use of each ET service, how it differs between the two ET arms, and perceptions of Elder Tree and the Clinician Report. We will also measure alcohol use, smoking, and falls.

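### The stated power above 80% belongs to the three-arm arm-by-time test and does not cover either adjacent 3-point difference, including ET-SS vs ET-LT

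*Combined protocol and SAP*

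**What the plan says.** All of this is in Section 6.0 of the combined protocol and SAP unless noted.

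- **Power for primary outcome.** The powering endpoint is pain interference (PROMIS T-score, SD 10), and 3 points is taken as clinically meaningful. The text states "We powered the analysis to be able to detect a 3-point difference" (d = .30) for control vs ET-LT, "and then the same magnitude of effect between ET-LT and ET-SS", which makes control vs ET-SS 6 points (d = .60). The result that follows comes from 10,000 mixed-model simulations at a post-attrition N of 255: power above 80% "to detect the study arm X time interaction".
- **Quantitative analysis plan.** Study arm is a three-level factor. The plan adds "We will conduct specific treatment X time contrasts both between, and within, groups to test time-based effects" and "For analyses that address the same hypothesis a Holm-Bonferroni correction will be applied". No power is given for any contrast.
- **Missingness.** The plan also says "we increased the total sample size after attrition to 291", to help with two moderators. Section 4.0 gives 291 as the number recruited.
- **Specific Aim 2 (Section 2.0).** The main hypotheses compare ET-SS with the other two arms. The plan adds "We also plan to compare ET-LT to the UC control", which is the other adjacent contrast.

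The alpha, the correlation between visits, the coding of time, the effect assumed at month 4 and the allocation ratio are not stated.

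**The concern.** The first sentence of the power statement names two pairwise 3-point differences as targets. The figure that follows is for one test of all three arms together. That test also draws on the assumed 6-point gap between control and ET-SS, so it can have high power while each 3-point comparison has little.

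This bears on the trial's main question. The Study Summary asks whether the smart system adds to what ET achieves, and Section 2.0 first names the comparison of ET-SS with the laptop version. A reader of Section 6.0 would conclude that a true 3-point advantage of ET-SS over ET-LT would be found more than four times in five.

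Section 2.0 also asks whether the two ET arms do equally well against control. The plan does not say how a non-significant ET-SS vs ET-LT contrast will be read. Someone who believes power was above 80% could take it as evidence of equality.

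**Working it through.** **Inputs from Section 6.0:** spacing d = 3 points, SD = 10, N = 255.

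**Assumed, because not stated:** 1:1:1 allocation (n = 85 per arm), two-sided alpha .05, equal correlation r between visits, shown at .3, .5 and .7.

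**Variance V per person of the quantity compared**
- Change from baseline to month 8: V = 2·SD²·(1 − r). At r = .5 this is 100.
- Month 8 adjusted for baseline: V = SD²·(1 − r²). At r = .5 this is 75.
- Mean of months 4 and 8 adjusted for baseline, with the full effect present by month 4: V = SD²·((1 + r)/2 − r²). At r = .5 this is 50.

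**Step 1: the plan's own figure.** The overall arm-by-time test with linear time (2 df) has noncentrality 2nd²/V. For change at r = .5 this is 2·85·9/100 = 15.3, giving 95% power. At r = .3 and .7 it is 85% and 99.7%. With categorical time (4 df) and a linearly growing effect, r = .5 gives 90%. Power exceeds 80% once r is above about .21 (2 df) or .36 (4 df). The stated figure is plausible for this test.

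**Step 2: what each pair contributes, with no assumption about r.**
- Overall test: 2nd²/V.
- Control vs ET-SS: n(2d)²/(2V) = 2nd²/V, the same value.
- Each adjacent pair: nd²/(2V), one quarter of it.

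| Overall power (2 df) | Overall noncentrality | Adjacent (one quarter) | Adjacent power |
|---|---|---|---|
| 80% | 9.63 | 2.41 | 34% |
| 90% | 12.65 | 3.16 | 43% |
| 95% | 15.44 | 3.86 | 50% |

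With 4 df the same overall powers allow at most 41%, 50% and 58%. For an adjacent contrast to reach 80% its noncentrality must be 7.85, so the overall value must be 4 × 7.85 = 31.4. That corresponds to overall power of about 99.95% at 2 df.

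**Step 3: ET-SS vs ET-LT with r assumed.** Power ≈ Φ(3/√(2V/n) − 1.96). For change at r = .5, √(200/85) = 1.534 and 3/1.534 = 1.956, which gives 50%.

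| Analysis | n per arm | r = .3 | r = .5 | r = .7 |
|---|---|---|---|---|
| Month 8, change | 85 | 38% | 50% | 71% |
| Month 8, baseline-adjusted | 85 | 54% | 62% | 78% |
| Mean of both follow-ups, adjusted | 85 | 74% | 79% | 90% |
| Month 8, change | 97 | 42% | 55% | 77% |
| Month 8, baseline-adjusted | 97 | 59% | 68% | 83% |
| Mean of both follow-ups, adjusted | 97 | 80% | 84% | 94% |

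The rows with 97 per arm treat all 291 as analysed (291/3 = 97). At 85 per arm, month-8 power reaches 80% at r of about .76 (change) or .72 (adjusted).

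**Step 4: check by simulation.** In 250 simulated random-intercept mixed models at r = .5, the overall test had 96% power, ET-LT vs control 50%, ET-SS vs ET-LT 54% and ET-SS vs control 98%. With 250 runs the simulation error on a figure near 50% is about 3 points (√(.25/250) = .032), so these agree with the formulas.

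**Step 5: Holm correction.** For change at r = .5, power for ET-SS vs ET-LT is about 42% if the family is all three pairwise contrasts. It is 49.6%, almost no loss, if the family is only the two ET-SS contrasts. The plan does not list the family.

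**Step 6: precision at r = .5, 85 per arm.**
- 95% CI half-width 1.96·√(2V/85): 3.0 points for change, 2.6 adjusted.
- Difference detectable with 80% power, 2.80·√(2V/85): 4.3 points for change, 3.7 adjusted.

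**The case against.** The strongest reply is that no figure in Section 6.0 is shown to be miscalculated. The 3-, 3- and 6-point sentence can be read as the pattern fed into the simulations, with the tested term named straight afterwards. The text does not use the word omnibus, and only the simulation code can settle which term was tested. This stands in part. However, the arm factor is defined with three levels, so the overall test is the natural reading, and the sentence on what the analysis was powered to detect claims more than an input pattern.

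A second reply is that 50% is an unfavourable choice. The correlation of .5 is not in the documents. Specific Aim 2 lists baseline outcomes among the covariates, and a mixed model uses partial data, so the effective n lies between 85 and 97. This also stands. It is why the 50% is conditional and why the full range is shown. But the plan does not say that baseline enters the primary model; adjustment appears under "Sensitivity analyses (with and without covariate adjustment". If the full effect is present by month 4 and both follow-ups are averaged with baseline adjustment, 80% is reached at r of about .52 with 85 per arm. With 97 per arm that scenario gives about 80% or more throughout. None of these conditions is stated as the basis of the power claim.

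A third reply is that the plan nowhere says a non-significant result will be called equality. That is correct. The point is that the plan leaves the reading open while stating an aim about equal effects.

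**Conclusion.** The concern holds. The power above 80% is credible for the three-arm arm-by-time test, but it does not establish power for control vs ET-LT or for ET-SS vs ET-LT.

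The firmest result is the one-quarter share. It needs only equal spacing, equal arms and the same model. A simulated overall power near the stated bound implies about 34% to 41% for each adjacent contrast, and even 95% overall implies at most 50% to 58%.

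Power for the platform comparison at month 8 with 85 per arm runs from 38% to 78% over r = .3 to .7, depending on r and on baseline adjustment. Assumptions about effect timing and analysed numbers can raise it to 94%, but the documents do not support choosing them. At r = .5, 80% power would need about 175 completers per arm for change, or 131 with baseline adjustment, against 85.

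At that correlation the confidence interval for ET-SS vs ET-LT would extend about as far as the clinically meaningful difference, so a non-significant result could not show that the platforms are equal. Because this is the power statement for the primary outcome on the trial's main comparison, it should be corrected.

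**What to change.** In Section 6.0:

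1. State, after confirming against the simulation code, that power above 80% at N = 255 applies to the overall study arm by time test.
2. Remove or qualify the claim that the study is powered for each adjacent 3-point difference.
3. Report from the same simulations the power and the detectable difference for ET-SS vs ET-LT. Give the visit correlation, time coding, effect assumed at month 4, baseline adjustment, allocation and alpha used, and name the Holm family. For orientation, the detectable difference at r = .5 is about 4.3 points unadjusted or 3.7 points baseline-adjusted.
4. State that a non-significant ET-SS vs ET-LT contrast will be reported with its confidence interval and will not be described as equal effects.

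The cost is wording, plus reading contrast power out of simulations that already exist. The stated power will look less favourable. No extra patients and no change of test are needed.

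### The missing-data sensitivity analysis allows best- or worst-case single fills without multiple imputation and fixes no values, by-arm rule or variance method, so it cannot support a robustness claim as written

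*Combined protocol and SAP*

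**What the plan says.** The Missingness paragraph of Section 6.0 states: "Data are likely to be missing not-at-random". It acknowledges that estimates may be biased as a result. The response is a sensitivity analysis: "Pattern-mixture modeling will test the sensitivity of our intervention analysis to missing data assumptions", carried out "by conducting sensitivity analyses after imputing missing data with a range of clinically plausible values using assumptions for missing data". The examples given are "best or worst case, with and without multiple imputation".

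The same paragraph expects "about 87% survey completion at 8 months", based on the previous trial, where "353 of 390 participants (90.51%) completed the 6-month survey" and "310 of 390 (79.49%) completed the 12-month survey". On the target effect, Section 6.0 says: "We powered the analysis to be able to detect a 3-point difference" between adjacent arms, on a T-score with SD 10. The planned difference between control and ET-SS is twice that.

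The primary analysis is intention-to-treat with a linear mixed model on the incomplete data. The plan gives no numeric best or worst value, no rule for applying fills by arm, no imputation model, no variance method for runs without multiple imputation, and no rule for reading results that disagree.

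**The concern.** The plan itself says the likely missingness mechanism is one under which its mixed model may be biased. The sensitivity analysis is the only stated safeguard, so it has to give an interpretable answer. Two of the permitted forms may not.

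- A single filled value analysed as if observed can overstate the information in the data.
- A best- or worst-case fill on a continuous score has no natural limit short of the ends of the scale. Depending on how it is applied by arm, the result can be set mainly by the value someone picked.

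Nothing is fixed in advance, so the choice could be made after the data are seen. A favourable run could then be cited as showing robustness, or an unfavourable one as refuting it.

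**Working it through.** **Inputs.** From Section 6.0: SD 10, a 3-point difference between adjacent arms, about 87% completion at month 8, post-attrition N of 255. From Section 4.0 (RCT Patient Recruitment): 291 randomised to three groups. Assumed: 1:1:1 allocation (97 per arm), two-sided 5% level, equal missingness m = 0.13 in each arm. The plan does not confine imputation to month 8; that is simply where it quantifies loss.

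**1. The plan's completion figure.** Interpolating between 353/390 = 90.51% at 6 months and 310/390 = 79.49% at 12 months gives 90.51 - (2/6) x 11.02 = 86.8%, matching the stated 87%. 291 x 0.87 = 253, close to the stated 255 (255/291 = 87.6%).

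**2. Single fill derived from the arm's own data (for example the arm mean).**
- Reported SE of a two-arm difference: 10 x sqrt(0.87) x sqrt(2/97) = 1.34.
- True SE, which rests on 0.87 x 97 = 84.4 observed per arm: 10 x sqrt(2/84.4) = 1.54.
- Ratio 1.34/1.54 = 0.87. The effective critical value is 1.96 x 0.87 = 1.71, a two-sided tail of about 8.8%.
- In 20,000 simulated null trials, rejection was 9.0% with arm-mean fill, 9.1% with the arm mean plus 5 and 8.4% with the arm mean plus 10. A baseline-adjusted simulation filling with the arm's own mean, regression prediction, 90th percentile or maximum gave 8.5-9.1%, with SEs about 12-15% too small.

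**3. Single fill not derived from the arm's data.** With preset constants 0, 5 and 10 points from the mean, used equally in both arms, the ratio of reported to true SE was 1.00, 0.995 and 1.01, and rejection was 5.0%, 5.4% and 5.0%. A carried-forward earlier score (correlation 0.5 assumed) gave 5.0%. Fills taken from the overall sample also kept about 5%.

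**4. Movement of the contrast.** If the filled values lie d1 and d2 points from their own arm means, the contrast changes by m x (d1 - d2).
- Opposite directions, distance D in both arms: 0.13 x 2 x D = 0.26 x D.
- One arm only: 0.13 x D.
- Equal shifts in the same direction: no change.

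| D (points) | Left of a 3-point difference, opposing in both arms | One arm only |
|---|---|---|
| 3 | 2.2 | 2.6 |
| 5 | 1.7 | 2.35 |
| 10 | 0.4 | 1.7 |
| 15 | -0.9 | 1.05 |

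**5. Where the point estimate reaches zero.**
- 3-point difference: 3/0.26 = 11.5 points (1.15 SD) in both arms, or 3/0.13 = 23.1 points (2.3 SD) in one arm.
- 6-point control versus ET-SS difference: 23.1 and 46.2 points.
- At the previous trial's 12-month loss of 20.5%, the 3-point figures fall to 7.3 and 14.6.

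**6. Where significance is lost.** This comes sooner. With SD 10 and no shift, z is already 3/1.54 = 1.95. With a residual SD of 7.1 (assumed, for a baseline-adjusted analysis) and the correct SE, z is 2.74 with no shift, 2.01 at opposing shifts of 3 and 1.52 at 5.

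**The case against.** The strongest reply is that the parenthesis only gives examples. The commitment is to pattern-mixture modelling over clinically plausible values, multiple imputation is among the planned runs, and delta-adjusted imputation is one form of what is already promised. A best or worst case is most naturally a preset value, and step 3 shows that a preset value used equally in both arms keeps the error rate near 5%. Bounding scenarios are also meant to depend on their assumptions.

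Much of this stands, and it rules out three stronger readings that a reader might infer.

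- *The error bars of the sensitivity analysis are wrong in general.* Not supported. The fault is confined to single fills computed from each arm's own data, and the plan does not name such a fill.
- *The plan fills in opposite directions by arm.* Not supported. The text has no by-arm rule, and equal shifts leave the contrast where it was.
- *The extremes can overturn any 3-point effect.* Not supported. That takes about 11.5 points in opposite directions in both arms, or 23.1 in one, and the plan limits itself to plausible values.

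What the reply does not answer is that the plan's wording permits both the sound and the unsound versions and does not say which will be run or which governs. Planning multiple-imputation runs as well does not settle this without a reading rule. The calculations above are two-arm comparisons at one visit, not the full arm-by-time model, so they show the mechanism and approximate size rather than exact operating characteristics.

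**Conclusion.** The concern holds as a weakness of the sensitivity analysis. With data-derived single fills, at 13% missing and 97 per arm, the SE is about 12-15% too small and a nominal 5% test rejects about 9% of the time. With opposing fills, the contrast moves 0.26 points for every point of fill distance, so an unstated choice of extreme can absorb most of a 3-point difference (2.6 points at a distance of 10). These sizes rest on 1:1:1 allocation, SD 10 and equal missingness across arms.

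A reader might go further and infer that the primary result is compromised. It is not: the mixed-model estimate uses none of these fills. The damage is to any statement that the result is robust to data missing not at random, which matters because the plan itself expects that mechanism.

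**What to change.** Replace the parenthesis of examples with one specified pattern-mixture analysis, delta-adjusted multiple imputation:

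1. Impute within arm from the available scores at months 0, 4 and 8.
2. Add a shift to the imputed scores, separately by arm and in both directions, over a grid stated in advance. The grid should extend until the tipping point or the limit of clinical plausibility is reached. A grid of 0 to 6 points is too narrow: used in one arm it moves a contrast by only 0.13 x 6 = 0.78. Opposing shifts of up to 12 points would cover a 3-point difference at 13% missing (0.13 x 24 = 3.1).
3. Fit the primary model to each completed data set and combine with Rubin's rules.
4. Report, for each arm contrast, the shift at which significance is lost, and state beforehand how that will be read.

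If a best- or worst-case run is kept, state its values and by-arm application in advance and label it an outer bound with no significance claim.

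The cost is SAP wording and slightly more programming. The sensitivity intervals will be wider than with single fills.

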### RCT Patient Recruitment

The RCT will involve 291 patients age 60 and older, recruited over 18 months, and randomized into three groups:

1. ET-SS: Patients will receive treatment as usual (TAU) + Smart System + Internet access + ElderTree
2. ET-LT: Patients will receive TAU + laptop + Internet access + ElderTree
3. Control: Patient will receive TAU

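### The 291 described as the sample after attrition, enlarged for two moderators, is the number randomised; attrition alone explains it, and the written analysis does not test the moderator hypothesis as worded

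*Combined protocol and SAP*

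**What the plan says.** **Sample size.** Section 6.0 (Power for primary outcome) reports: "Across 10,000 LMEM simulations, a post-attrition" N of 255 gives more than 80% power "to detect the study arm X time interaction". The Missingness paragraph expects "about 87% survey completion at 8 months", based on an earlier trial of the same intervention. It continues: "Thus, we increased the total sample size after attrition to 291 to increase the likelihood of detecting effects on the outcomes with 2 moderators", naming sex and number of chronic conditions. Section 4.0 (RCT Patient Recruitment) states: "The RCT will involve 291 patients age 60 and older", randomised into three groups.

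**Moderators.** Hypothesis 4 (Section 2.0, Specific Aim 2) says that ET-SS, compared with ET-LT and control, "will show greater improvements for a) women (vs. men"), for patients with more chronic conditions, and for "patients with fewer barriers to using technology for the primary and secondary outcomes". In the analysis plan the mixed models "examine effects of study arm (ET-SS vs. ET-LT vs. control, a between-subjects factor) on our outcomes over time". Moderators enter only in the following paragraph, as acting on the indirect paths of structural equation models (SEMs) whose outcomes are the two primary ones. That paragraph refers the reader to Figure 1, which is not available in the text reviewed.

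**The concern.** The number 291 is given two roles that cannot both hold: everyone randomised, and those remaining after attrition. The sentence also says that patients were added so that moderator effects could be detected. A funder or reader would take this to mean the trial was enlarged for subgroup questions, yet no moderator effect size, interaction power or separate increment appears anywhere.

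The second matter stands apart from the arithmetic. A prediction that one group improves more under ET-SS concerns the arm effect itself. A moderated indirect path is a different quantity: it asks whether the part of the effect passing through a mediator varies between groups. If the text is followed as written, the stated hypothesis is not tested, and for secondary outcomes there is no moderation analysis to follow.

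**Working it through.** **1. Attrition arithmetic (documented figures only)**

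Inputs: 255 after attrition, 87% completion, and earlier-trial completion of 353/390 at 6 months and 310/390 at 12 months (Section 6.0); 291 randomised (Section 4.0).

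- Completion rate: 353/390 = 90.51% and 310/390 = 79.49%. Linear interpolation to 8 months gives 90.51 − (90.51 − 79.49) × 2/6 = 86.8%, which reproduces the plan's 87%.
- Expected 8-month completers: 291 × 0.87 = 253.2.
- Number to randomise for 255 completers: 255/0.87 = 293.1. Per arm, 85/0.87 = 97.7; rounding down gives 97 × 3 = 291, rounding up 98 × 3 = 294.
- Implied retention: 255/291 = 87.6%.
- Step to explain: 291 − 255 = 36. Expected loss: 291 × 0.13 = 37.8. Nothing is left over for moderators.
- If 291 were truly the number after attrition: 291/0.87 = 334.5, so about 335 randomised, 335 − 291 = 44 more than planned.

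**2. Could 255 already contain a reserve?**

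The plan does not give the within-person correlation, alpha or allocation ratio. I assume two-sided 0.05, 1:1:1 allocation, SD 10 at each visit, 8-month changes of 0/3/6 points across arms, and correlation r = .3/.5/.7. The SD of change is 10 × √(2(1 − r)) = 11.83/10.00/7.75.

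| Test | r = .3 | r = .5 | r = .7 |
|---|---|---|---|
| Overall test on 0-to-8-month change (2 df), power at 255 | 85% | 95% | >99% |
| Smallest N for 80% | 228 | 165 | 102 |
| Overall test, three categorical visits (4 df), linear effect, equal correlations: smallest N for 80% | 282 | 204 | 123 |
| One adjacent pair of arms, 3 points, 85 per arm: power | 38% | 49% | 71% |

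A reserve is possible for the overall arm × time test, but it depends on the correlation and on which test was simulated. The plan settles neither.

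**3. Hypothesis against analysis**

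- Moderators: hypothesis 4, Table 2 and the SEM paragraph list three; the sample-size sentence names two.
- Effect: hypothesis 4 concerns the arm effect; the SEM paragraph concerns indirect paths.
- Outcomes: hypothesis 4 covers primary and secondary; the SEM paragraph covers the two primary.
- Mixed models: arm and time, with no moderator term in the text.

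**4. What interaction could be detected**

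For one pair of arms, 85 per arm, and a binary moderator split evenly (p = .5):

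SE = SD of change × √(2[1/(np) + 1/(n(1 − p))]) = SD of change × √(4/42.5) = 3.63/3.07/2.38 for r = .3/.5/.7.

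- Detectable difference at 80% power, 2.80 × SE: 10.2/8.6/6.7 points.
- Power for a 3-point interaction, Φ(3/SE − 1.96): 13/16/24%.
- Power for a 6-point interaction (as large as the planned control vs ET-SS difference): 38/50/71%.

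These figures suit sex and the 4-5 vs 6+ category if evenly split. They do not cover the two-item barriers measure.

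**The case against.** The most natural defence is that the phrase means after allowing for attrition. It comes directly after the completion rate, and this reading is reasonable. It repairs the label, but the sentence still says the sample was raised for moderators, while the allowance for loss uses the whole step.

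A second defence is that 255 may exceed the minimum for the overall test. That stands as a possibility. A reader might infer that the moderator rationale is false; the documents support only that it is undocumented. A reader might also infer that the trial is short of patients for its primary analysis or ought to randomise 335. That does not follow: 253 and 255 are practically the same, and the mixed models also use partial data, such as a 4-month survey from someone missing at 8 months.

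On hypothesis 4, Figure 1 is cited for moderation and may draw direct paths for the primary outcomes. It would therefore go too far to say that direct moderation is planned nowhere, or that a model will necessarily be picked once results are known. The firm part is that the text provides no moderation analysis for secondary outcomes and no moderator term in the mixed models.

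Finally, hypothesis 4 could simply be reworded to match the SEMs. That would make the plan consistent, but it would withdraw the claim on secondary outcomes and replace the subgroup question with a different one.

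**Conclusion.** Both parts hold, as matters that should be corrected and that do not threaten the primary analysis.

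1. The 291 is the number randomised. About 253 are expected at 8 months, against 255 used for power, and no moderator increment is documented. This rests only on the plan's own figures, and confidence is high.
2. The text of Section 6.0 does not test hypothesis 4 as worded. Confidence is high for the secondary outcomes; for the primary outcomes it is qualified by the missing Figure 1.

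Power for moderation is limited rather than uniformly negligible: 13-24% for a 3-point pairwise interaction, 38-71% for 6 points, under the assumed SD, correlations, even split and 85 per arm.

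**What to change.** 1. In Section 6.0, state 291 randomised and about 253-255 expected with 8-month data. Delete the statement that the sample was increased for moderators, unless the calculation is shown: what number was raised, by how much, and for which interaction.
2. As the test of hypothesis 4, add arm × time × moderator terms, with all lower-order terms, to the (generalised) mixed models for the primary and secondary survey outcomes. For 8-month ET use, once its definition is final, add an arm × moderator term within the two ET arms. Label these exploratory and keep the SEM moderated mediation as a separate question. If Figure 1 already shows moderated direct paths, say so in the text and name the outcomes covered.
3. For condition count, use the 4-5 vs 6+ randomisation stratum. Section 5.0 and Table 2 take the count from electronic health records, but Patient Consent limits record collection to UW Health patients, so the count from that source would be missing for community recruits. The stratum exists for everyone randomised.

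**Cost.** No extra patients and no new data. Three moderators × 11 outcomes (2 primary, 8 secondary survey, 1 ET use) gives at least 33 exploratory tests. Physical quality of life and pain intensity each list two instruments; scoring these separately adds 2 outcomes, so 3 × 13 = 39. The stratum discards detail from the full count, and with the power shown above the moderator claim has to be stated more modestly.
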